## **DATA GATHERING:**

### **Study Outcomes:**

Based on the primary study objective, the key data to be collected prospectively after the trial begins is the number of patients diagnosed with microbiologically confirmed Pulmonary TB (index cases) (also will collect number of not confirmed pulmonary and not pulmonary), the number of identified household contacts of these index cases with confirmed pulmonary TB, and the number of household contacts who started LTBI therapy. Note that the number who actually complete therapy is not required as this is a secondary outcome that occurs later and data will be collected retrospectively. The primary study outcomes of number of index cases, number of household contacts identified and the number of household contacts starting LTBI therapy must be measured every month at all health facilities (Intervention and Control) throughout the trial. Outcomes will be recorded using a standardized form. More detail on data sources and how to ascertain study outcomes is provided below.

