#### **Sample size considerations:**

As seen in Table 1 above (Study population), we estimate that during the 18 months of the study, 2475 active TB cases will be diagnosed at the participating sites, and 10,425 contacts will be identified, of whom 4975 will be diagnosed with LTBI. We wish to detect a 15% increase in the proportion of contacts that initiate therapy, with a level of statistical significance of 0.05 (alpha error). The intra-class correlation coefficient (ICC) which describes the inter-cluster heterogeneity, (or analogously the correlation amongst subjects in the same cluster) has less effect, but to be conservative we will assume this to be 0.05 to 0.1– which is high. In data from the 9INH vs 4RIF trial (comprising 6031 adults treated for latent TB in 12 centres), the ICC for the centre effect was low – just 0.01-0.02, depending on the method used to estimate it, for treatment completion. We will have 24 clusters in 5 countries. Our power calculations are based on the number of close contacts identified per randomization unit (from Table 1).

**Table 2: Detectable differences with all sites in all countries** (alpha=.05, and Power = 80%)

Proportion starting LTBI therapy in Control Arms	N Contacts per clinic	Design Effect	Total sample size per arm	Intra-Class Correlation	Detectable difference
0.10	100	2.0	1222	0.01	0.05
0.10	100	6.0	1214	0.05	0.10
0.10	100	10.9	1199	0.10	0.14
0.30	100	2.0	1236	0.01	0.08
0.30	100	6.0	1261	0.05	0.13
0.30	100	10.9	1221	0.10	0.18

Therefore, given 24 clusters in 5 countries, with at least 100 contacts per site every 6 months (based on minimum 40 active cases every year, and estimated 4.2 contacts per index case), and assuming that at baseline only 10% of contacts are started on Latent TB therapy, plus an ICC of 5%, we would have 80% power to detect a 10% increase in proportion of contacts starting therapy. If the number of contacts per site is higher this will actually have a modest effect on the detectable difference. If the proportion starting therapy is much higher (30%), then the detectable difference would be near 13%.

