The resources and prior staff experience in LTBI care at the Canadian sites are very different from that of the sites in the LMIC. This makes it likely there will be better pre-intervention outcomes in Canada, potentially limiting the need for, and impact of certain interventions. The other 5 countries are also different – with regard to resources, availability of trained health workers, and patient populations. This may result in large differences in the baseline situation, and intervention effect size. Hence secondary analysis is planned to estimate the intervention effect within each country. Since Canada has the smallest numbers we estimated the power to detect differences in Canada alone, as shown in Table 3.

**Table 3: Detectable differences in Canada alone** (alpha=.05, and Power = 80% )

Proportion starting LTBI therapy in Control Arms	N Contacts per clinic	Design Effect	Total sample size per arm	Intra-Class Correlation	Detectable difference
0.30	50	1.5	150	0.01	0.19
0.30	50	3.5	150	0.05	0.29
0.30	50	5.9	150	0.10	0.37
0.30	100	2.0	300	0.01	0.16
0.30	100	6.0	300	0.05	0.27
0.30	100	10.9	300	0.10	0.36

Therefore in Canada, we should have sufficient power to detect a 27% increase in proportion of infected contacts starting LTBI therapy, if 30% now start therapy. Increasing the number of contacts per cluster (clinic) to 300 would only decrease the detectable difference to 25%.

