### **RANDOMIZATION:**

As described earlier in the Study Design section, the sites which receive the intervention of Phase 1 followed by Phase 2 will be selected randomly. Randomization will be stratified by country (See again Figure 3). As much as possible, within each country, the randomization of sites must result in reasonable balance in the number of contacts managed with and without the intervention. Because the number of patients with newly diagnosed pulmonary TB is not the same at all sites, a special procedure to ensure optimal balance will be undertaken. A total of 1000 randomization sequences will be generated (using a computer programme developed by [name] – biostatistician for this project). Each sequence will then be examined to verify the resultant balance in contacts who will and won't receive the interventions. Randomizations that result in reasonable balance will be selected. (In other studies this has meant approximately 200 of the 1000 randomization are selected). In the final step, one sequence is randomly selected from this sub-group of balanced randomization sequences.

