**DATA ANALYSIS FOR PHASE 2****Contact investigation outcomes:**

Among the household contacts, the following outcomes will be measured

1. Contacts identified.
2. **Started LTBI therapy** (primary outcome)
3. Completed LTBI therapy (secondary outcome)

The primary outcome will be the proportion of identified contacts who start LTBI therapy – in the final 6 months of the trial (to account for delayed impact of this complex intervention). If we find that more than 20% of contacts are diagnosed to have active TB, which would be far in excess of published experience, then we would investigate if this reflected over-diagnosis.

Our analysis will be performed at the level of the individual, but will account for correlation between subjects from the same centre. Population averaged logistic regression with an identity link estimated via generalized estimating equations (GEE) and using a jack-knife estimate of the variance will be used to assess the effect of the intervention on the primary and secondary outcomes above, depending on the type of outcome (e.g. count or proportion). This approach will account for the correlation between subjects in the same cluster, and for varying cluster sizes. Using an identity link (rather than a logit link) will allow us to estimate risk differences for binary outcomes.

Population averaged models estimated via GEE are robust to mis-specification of the correlation structure. While our data will surely have clustering at the household level as well, we need only account for the top-level cluster (here centre) and use the empirical standard errors to ensure that our inferences are conservative.

For count type outcomes, we will use a similar approach as described above, but using a Poisson distribution.

In secondary analyses, we will use logistic regression with a logit link estimated via GEE and also adjust for additional confounders (country, age, sex and smear status of index case). In sensitivity analyses we will analyze at the level of the cluster. Missing data will be dealt with via multiple imputation using chained equations which will allow us to impute binary as well as continuous variables .

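### The primary risk-difference model omits country, the randomisation stratum, so its intervals are too wide if countries differ; the size of the loss depends on inputs the protocol does not settle

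*Protocol*

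**What the plan says.** The Randomization section states "Randomization will be stratified by country", and Study design says the same. Sample size considerations describes how the countries differ in resources, staffing and patients, and adds: "This may result in large differences in the baseline situation, and intervention effect size".

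Data analysis for Phase 2 fixes the primary analysis: an identity-link model for the risk difference, estimated by GEE, with centre as the cluster and a jack-knife variance. No country term is named. Country appears with age, sex and smear status one step later: "In secondary analyses, we will use logistic regression with a logit link estimated via GEE and also adjust for additional confounders". A cluster-level analysis is planned as a sensitivity analysis, with no covariates named, and within-country estimates are planned as secondary. So no country-adjusted risk difference is planned across the trial. The Data Analysis section of the cross-over study repeats the same wording.

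The power statement rests on these inputs: "We will have 24 clusters in 5 countries", "with at least 100 contacts per site every 6 months", a control proportion of 10%, an ICC of 0.05 and a difference of 10 points at 80% power. For Canada alone the control proportion is put at 30%.

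**The concern.** Stratified allocation puts half the clinics of each country in each arm, so differences between countries cancel out of the treatment contrast. An analysis that ignores country does not know this. It treats the spread between countries as random variation between clinics and adds it to the standard error. The reported precision is then worse than the design delivers. With 24 clusters precision is scarce, and the protocol itself notes that more contacts per site would help only modestly.

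This is not a detail left open for a later analysis plan. The protocol says where country enters, and it is outside the primary model.

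**Working it through.** **1. The protocol's own figure.** Design effect = 1 + 99 × 0.05 = 5.95. For 10% against 20%, two-sided 0.05 and 80% power, n per arm before clustering = [1.96√(2 × 0.15 × 0.85) + 0.84√(0.09 + 0.16)]² / 0.10² = 199. Then 199 × 5.95 = 1184, against 1214 in Table 2. At 1214 the power is 0.81, so the row reproduces. It uses a single ICC and no country term. I take 24 clusters as 12 per arm.

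**2. Standard error with and without country.** Let V_w be the within-country variance of a clinic's proportion, mean p(1−p) × [ICC + (1−ICC)/m], and V_c the variance of the country rates across clinics. Then SE with country ≈ √(2V_w/12), and SE without country ≈ √(2(V_w+V_c)/12).

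Assume Canada (4 clinics) at 0.30, the other 20 clinics at 0.10, a true difference of 0.10, m = 100 and a within-country ICC of 0.05:
- Mean p(1−p) = 0.110 in control and 0.173 in intervention clinics, average 0.142.
- V_w = 0.142 × 0.0595 = 0.0084.
- V_c = (4/24)(20/24)(0.20)² = 0.0056.
- Ratio = √(1 + 0.0056/0.0084) = 1.29.

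Simulation (beta-binomial clinics, stratified allocation, jack-knife, exchangeable weights) gives 0.0486 without and 0.0376 with country, also 1.29. Further ratios at the 10-point effect:

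| Control rates (assumed) | ICC 0.01 | ICC 0.05 | ICC 0.10 |
|---|---|---|---|
| No country difference | 0.98 | 0.98 | 0.98 |
| Canada 0.20, others 0.10 | 1.23 | 1.07 | 1.03 |
| Canada 0.30, others 0.10 | 1.74 | 1.29 | 1.16 |
| As above, Table 1 sizes, independence weights | 1.51 | 1.08 | 0.99 |

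The Table 1 sizes per 6 months are one third of the 18-month contacts divided by clinics: Canada 1575/12 = 131, Benin 3150/6 = 525, Ghana 1900/6 = 317, Indonesia and Vietnam 1900/24 = 79.

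**3. Power, Canada 0.30 and ICC 0.05.** Without country (22 df, t = 2.074) the estimate must exceed 2.074 × 0.0486 = 0.101, just above the true 0.10, so power is about 50%. With country (24 − 6 = 18 df, t = 2.101) the threshold is 2.101 × 0.0376 = 0.079, and (0.100 − 0.079)/0.0376 = 0.56, so power is about 71%. Clinic-level regression with Table 1 sizes gives 50% and 72%. Type I error without country is about 1%. With no country difference, clinic-level power is 76% without and 75% with country.

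**4. What the ICC of 0.05 contains.** Rates of 0.30 in 4 clinics and 0.10 in 20 average 0.133. The country contrast alone implies an ICC of 0.0056/(0.133 × 0.867) = 0.048. If 0.05 is meant as the total, little is left within country. At a within-country ICC of 0.01, power is 0.80 without country and 0.99 with it.

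**5. Jack-knife scaling.** The jack-knife figures above scale the variance by (K − p)/K, with K clusters and p parameters. Scaling by (K − 1)/K multiplies the adjusted SE by √(23/18) = 1.13 and the unadjusted SE by √(23/22) = 1.02. The ratio 1.29 falls to 1.29 × 1.02/1.13 = 1.16, and a run on Table 1 sizes gives power of 47% against 61%. With no country difference the ratio is 0.98 × 1.02/1.13 = 0.88, so adjustment would then widen the interval.

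**The case against.** The strongest reply is that nothing invalid happens. The estimate is unbiased, the error is on the conservative side, and country-adjusted and within-country results will be seen in secondary analyses. All of that stands. But the protocol's stated wish for conservative inference concerns household clustering. It gives no reason to discard the precision bought by stratification.

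A second reply is that the country contrast is not established. The sentence after Table 3 ties Canada's 30% to infected contacts. Read literally, with 450 of 1575 Canadian contacts infected, it becomes 0.30 × 450/1575 = 8.6% of identified contacts, close to the 10% assumed overall, and the loss almost vanishes. The header of Table 3 does not say infected, so both readings are open. No other country's rate is given. This limits the size that can be claimed, not the direction.

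Three stronger readings are tempting and not supported:
- **Intervals about 40% too wide.** That ratio (1.40) arises for an unadjusted clinic-level analysis with Canada at 30%, ICC 0.05 and no treatment effect. At the 10-point effect the same analysis gives about 1.31. The protocol supplies no figure of this kind.
- **The planned 80% power is missed because of this.** That follows only if the assumed ICC of 0.05 is a within-country value. The protocol describes it as heterogeneity between clusters and does not say whether country is included.
- **Each clinic's early rate should also be a covariate.** Outcomes "must be measured every month at all health facilities (Intervention and Control) throughout the trial", so the data would exist. But they are collected after randomisation, during an evaluation that is part of the intervention and is carried out only at intervention sites.

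**Conclusion.** The point holds as a mismatch between design and primary analysis that costs precision, not validity. Its size is conditional: nothing if countries do not differ; up to about 10% on the standard error for a 10-point Canadian excess at a within-country ICC of 0.05; about 30% for a 20-point excess with exchangeable or clinic-level weighting (about 27% on interval width, since 1.29 × 2.074/2.101 = 1.27); about 8% for that excess with independence weights and Table 1 sizes. If 0.05 is the total ICC, planned power is roughly kept and only extra power is forgone.

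These figures assume 10% in every country other than Canada, a constant risk difference, beta-binomial clinics, and no effect of the further restriction of the randomisation on contact numbers. The protocol names neither the working correlation nor the jack-knife scaling. The figures apply to the 18-month trial; the cross-over comparisons are between periods at the same clinics, so these sizes do not carry over to them.

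**What to change.** In Data analysis for Phase 2, include country as a fixed effect in the primary identity-link risk-difference model, and refer the test and interval to a t distribution on clusters minus parameters (24 − 6 = 18). Adjust the planned cluster-level sensitivity analysis for country as well; it is a useful check because Benin and Ghana have only two clinics each. State the working correlation and the jack-knife scaling, since both affect what the adjustment gains. State also whether the ICC in the sample size section includes variation between countries. Carry the wording into the cross-over section or say why it differs there. Do not adjust for the Phase 1 clinic rate.

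The cost is a few sentences and no new data. Adjustment uses 4 degrees of freedom and, if countries turn out alike, about one point of power with clinic-level analysis or with exchangeable weights and (K − p)/K scaling. With independence weights or (K − 1)/K scaling the cost would be larger, which is why both choices should be named in advance.

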### **Study design:**

We propose a cluster randomized trial at 36 sites in 6 countries. Sites randomized to the intervention group will receive a complex two-phase intervention lasting 18 months. Control sites will receive a stream-lined version of this 2-phase intervention after 18 months, while outcomes are continued to be measured at all sites for an added 12 months.

**Randomization** will be stratified by country, and restricted to ensure equal number of participants receiving or not receiving the intervention within each country. Following randomization, **in Phase 1**, a standardized public health evaluation will be conducted at all intervention sites to identify barriers to LTBI diagnosis and treatment initiation, in order to select the solutions to be used in Phase 2. This will include measurement of the key study outcomes (see below). To ensure standardization of data gathering we will use (i) current indicators of the LTBI cascade of care in the participating units (number of contacts per index case registered, investigated, started on treatment and completing treatment) and (ii) interviewer-administered standardized questionnaires – for patients with newly diagnosed active pulmonary TB, household contacts of these patients, clinic staff and administrators. These questionnaires will assess management of contacts, LTBI diagnosis and therapy, as well as TB-related knowledge, attitudes and beliefs from the perspective of these different participants. Results from this phase will be analysed, and used by the investigators, together with local public health officials, to decide on appropriate corrective solutions. In control sites we will gather data on study outcomes only (see below).

**In Phase 2**, solutions will be selected, and implemented at the intervention sites. Preparations and training of staff at each site will be conducted before the intervention begins, as soon as each site (clinic) is judged ready to begin. Study outcomes will continue to be measured at all sites through-out Phase 2.

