### **Ascertainment of study outcomes - at all sites:**

Ultimately, in the intervention sites we will be able to use the newly developed and introduced Contact Management Registries (see below) to extract all necessary information and outcomes – including number of pulmonary TB cases (Index cases), number of contacts identified, and number who initiate LTBI therapy. However, these detailed contact registries are considered an integral part of the public health intervention, since considerable training in recording and reporting as well as the procedures of contact management will be needed for these to be completed accurately and completely. Introduction of these registries at control sites would be difficult without extensive training; if such training was given at the control sites, this would constitute a partial intervention, and reduce potential differences between intervention and control sites.

Hence recording of outcomes at control and intervention sites must rely on simple measures that can be implemented with minimal training, prior to the start of the trial at all sites. It is important that the procedures to ascertain (measure) these outcomes be established at the beginning of Phase 1, and continue **unchanged** at all health facilities (both intervention and control facilities) through-out the 18 months of the study.

Identification of contacts may not be performed, or not clearly recorded at all health facilities – especially the control facilities. This is why we must carefully document the number of index patients with active pulmonary TB diagnosed at each site. When the study is completed, the coordinating centre may use the number of index cases to estimate the number of household contacts that likely could have been identified (see Analysis section) Data sources will vary by site, depending what methods of documentation are already being used. We will collect information on the number of newly diagnosed index cases from lab or other sources that report active cases. The number of household contacts indentified will come from different sources depending on what is available the site. Finally, we will estimate the number of contacts who start LTBI treatment from hospital and or clinic records using a standard data collection form in all sites. The number of contacts completing LTBI therapy will be estimated retrospectively from clinic records.

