**PHASE 2 ENHANCED REPORTING:**

**Contact Management Registries**

A new registry book will be developed to record the key diagnostic and treatment steps in contact management. To facilitate their later adoption by health facilities as part of routine TB control activities, these contact registries will be modeled after the Active TB Treatment Registries of national TB programs that are currently used in all DOTS programmes and recommended by WHO .

The Contact Registry will include identifying information for each new patient with active pulmonary TB, as well as identifying, and demographic information for all identified contacts. The results of screening tests, plus Chest X-ray and medical evaluation for the TST (or IGRA) positive contacts will be included, as well as initiation and completion of LTBI treatment. Information on LTBI treatment starts from these registries will be compared to the other methods of ascertainment of the primary outcome – in the final 6 months – in secondary analysis

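### The adjusted secondary model needs age, sex and index-case smear status, but the protocol schedules none of them at control clinics during the 18-month trial

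*Protocol*

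**What the plan says.** **Analysis.** In the Protocol, under Data Analysis for Phase 2, "Our analysis will be performed at the level of the individual". A secondary logistic model will "also adjust for additional confounders (country, age, sex and smear status of index case"). One general sentence covers gaps: "Missing data will be dealt with via multiple imputation using chained equations". The Data Analysis section of the cross-over study repeats this plan.

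**Collection.** Study design states: "In control sites we will gather data on study outcomes only (see below"). Study Outcomes defines these as the "number of index cases, number of household contacts identified and the number of household contacts starting LTBI therapy", which "must be measured every month at all health facilities (Intervention and Control) throughout the trial". The Ascertainment section says "recording of outcomes at control and intervention sites must rely on simple measures that can be implemented with minimal training" and requires the procedures to stay unchanged for 18 months. It keeps the Contact Management Registries out of control clinics because the training they need would be a partial intervention. Those registries hold information on each index patient, "as well as identifying, and demographic information for all identified contacts".

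**The concern.** The analysis asks for person-level covariates, while the collection plan for one arm provides totals. Totals are enough to rebuild starters and non-starters by clinic, so the unadjusted comparison can be made. They cannot support adjustment for age, sex or smear status.

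This is not ordinary sporadic missingness, because it would coincide with treatment arm. The imputation sentence gives the impression that such gaps can be repaired. If the model were run on that basis, the adjusted effect and its interval would reflect the imputation model and carry no information about confounding between arms. With few clusters, readers will look to the adjusted result for reassurance about chance imbalance.

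**Working it through.** The plan gives no figure to reproduce. The check traces each covariate to its source and then asks whether imputation could fill the gap.

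**Step 1. Scheduled source by arm during the 18-month trial**

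| Covariate | Intervention clinics | Control clinics |
|---|---|---|
| Country | known for every site | known for every site |
| Contact age, sex | Contact Registry | none scheduled |
| Index-case age, sex | not itemised; registry identifies the index patient | none scheduled (number of cases only) |
| Index-case smear status | not named among registry contents | none scheduled (number of cases only) |

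No other data stream closes the gap. The cascade review and the questionnaires are confined to intervention facilities. Time-and-motion work does reach control facilities, but it measures staff time. Control clinics receive the registries only in Phase 2 of the cross-over. Smear status is a real variable here, since index cases may be confirmed by smear, culture or both.

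**Step 2. Can imputation recover it?** Let X be a covariate seen only in the intervention arm, Y the start of treatment and T the arm. The imputation model regresses X on (1, Y, T) in the rows where X is observed. Every such row has T = 1, so the T column duplicates the intercept. The design has rank 2 of 3, and the arm term cannot be estimated.

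If T is simply dropped, X is drawn from the intervention arm's P(X | Y). The joint distribution then becomes P(T, Y, X) = P(T, Y) × P(X | Y). Within any level of X, the P(X | Y) factors cancel from the T–Y odds ratio. Apart from imputation noise, the adjusted odds ratio is forced back to the crude one whatever the truth, and would look like evidence of no confounding.

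**Step 3. How much could the answer move?** Assumed inputs, none from the protocol:
- risk of starting 20% (intervention) and 10% (control);
- a binary covariate with 35% prevalence in the intervention arm;
- covariate–outcome odds ratio 3 in both arms.

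For each arm, solve for a in: risk = π·expit(a + ln 3) + (1 − π)·expit(a), where π is the covariate prevalence. The adjusted odds ratio is exp(a₁ − a₀). The crude odds ratio is (0.20/0.80)/(0.10/0.90) = 2.25.

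| Assumed control prevalence π | Adjusted odds ratio |
|---|---|
| 15% | 1.78 |
| 25% | 2.05 |
| 35% | 2.32 |
| 45% | 2.61 |
| 55% | 2.89 |

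The observed data are identical in every row. Only the unobserved control prevalence changes.

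**Step 4. Cross-over comparisons.** The first compares the original intervention clinics in two periods, both with registries, so contact demographics exist in both. The second compares the former control clinics before and after they receive registries. There the covariates would be unobserved for the whole earlier period, and Step 2 applies with period in place of arm.

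**The case against.** **The form is not shown.** Outcomes go on a standardized form used at all sites. Its fields are not in the protocol text, and Study Outcomes lists only key data. A reader might infer that every control record will certainly lack these covariates. The documents do not support that: the gap follows from what is scheduled, and control laboratory or clinic records may well hold the items. This stands as a limit on the wording. It does not supply a planned source.

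**The covariates may all belong to the index case.** On that reading, the items are likely to be in the treatment and laboratory registers. Index cases must be counted from such sources in both arms anyway. This also stands, and it makes the repair easier. Even so, the protocol extracts only the number of cases.

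**The statistical analysis plan can settle it.** It can choose covariates, but it cannot create data. Ascertainment is fixed at the start of Phase 1 and must not change, so collection has to be decided in the protocol.

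**Other sections say outcomes come from Contact Registries.** Rationale for study design and the Phase 2 timetable do say so. The Ascertainment section rules this out for control clinics during the trial. The passages need reconciling, but they do not rescue the model.

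**The imputation sentence is generic.** True: it does not say that a variable missing for a whole arm will be imputed. It does not exclude it either.

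**Conclusion.** The point holds as a mismatch between planned collection and planned analysis. As scheduled, age, sex and index-case smear status would be unobserved in the control arm. The adjusted secondary model would then either lose that arm or rest on an imputation that cannot identify the covariate's relation to arm. This non-identifiability needs no numerical assumption. The 1.78 to 2.89 range does, and serves only as illustration.

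The reach is limited. A reader might infer that the primary result is compromised. It is not: the unadjusted primary analysis works from counts by clinic, the cluster-level sensitivity analysis needs no individual covariates, and country is known everywhere. Nor does the problem extend to the whole cross-over analysis, because only its second comparison shares it.

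A reader might also size the loss by halving the expected contacts in Table 1. That is not supported either, since the protocol itself warns that contacts may go unidentified or unrecorded, especially at control clinics. The number of control contact records is unknown.

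This should be corrected before Phase 1, as a defect of a secondary analysis.

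**What to change.** Choose one of two routes and say whose age and sex are meant.

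**(a) Collect the covariates.** Before Phase 1, add to the standardized form, identically in both arms, one non-nominal line per index case: age, sex, smear status, contacts identified and contacts starting treatment. Define the adjustment covariates as index-case characteristics. The cost is a few register fields per case, plus the work of linking contacts and starts to their index case at control clinics. That linkage is not now planned, because the three counts come from separate sources that vary by site. Contact-level age and sex are given up.

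**(b) Restrict the model.** Limit the adjusted model in the Phase 2 analysis, and in the second cross-over comparison, to country and clinic-level covariates held in both arms or periods. The first cross-over comparison can keep contact demographics. The cost is wording only, with individual-level adjustment given up.

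Under either route:
- state that a variable unobserved in a whole arm or period will not be imputed;
- name the source of smear status, which is not listed even among the registry contents;
- reconcile the sections that describe registries as the outcome source with the Ascertainment section.
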